The combination of ixazomib and lenalidomide has been studied as maintenance therapy post autologous SCT.²⁷ This phase II trial enrolled 64 patients with a median age of 60 (range 39-74); 34 remained on therapy as of May 2017 having received a median of 28 cycles (range 1-51). Best overall response included stringent Complete Response (sCR 7.8%), CR (26.5%), VGPR (53%) and PR (10.9%). 29 patients had an improvement in their best overall response from their baseline response. The median PFS had not been reached with a median follow up of 37.8 months; estimated 2-year PFS is 81%. 30 patients are off study: 16 due to progressive disease (PD), 3 at PI discretion, and 11 due to consent withdrawal. 22 patients had G1/2 peripheral neuropathy (PN); 6 patients had G3 PN. 16 patients required a dose reduction to 2.4 mg for PN (8), neutropenia (3), hearing loss (2), rash (1), thrombocytopenia (1) and 4 patients discontinued ixazomib for neuropathy (2), neutropenia (1), and thrombocytopenia (1). 15 patients had a dose reduction of Len to 10 mg for 21 days of a 28-day cycle, while 9 patients had a dose reduction to 5 mg for 28 days.

We selected ixazomib as the intervention in this trial for several reasons:

1. Ixazomib appears to be at least as effective when used in combination with lenalidomide and dexamethasone in newly diagnosed myeloma, when comparing the results of the C16005 trial with the published data with VRd. Patients coming on this trial would have received on average four cycles of bortezomib containing regimen (VRd or VCd) as induction prior to stem cell transplantation, and hence would be relatively PI naïve. To further allay the concerns of the steering committee, we have now excluded any patient who progressed on a bortezomib-containing regimen pre-SCT or were primary refractory. This is likely to be a small population considering the high response rate with VRd and VCd.²⁴
2. Ixazomib has the added advantage of being taken orally, and making it more convenient and acceptable for a patient who has been on oral maintenance for a year and now may be hesitant to come back in weekly for an injectable medication. An integrated analysis of ixazomib maintenance across 4 different studies was presented recently demonstrating a continued increase in depth of response with continued treatment, with excellent tolerability.²⁸ The phase III trial of ixazomib maintenance versus placebo was recently announced to show a PFS benefit for ixazomib.

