6.1 Response Considerations

The International Myeloma Working Group (IMWG) uniform response criteria will be adapted to assess response to therapy in this trial.^{4,44} Since patients are entering the study at end of defined duration of therapy, and baseline disease parameters may not be known, we will limit the assessments to categories that are independent of baseline values (i.e., MRD negative, sCR, CR, and VGPR as defined below).

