6.2.1.1 Sustained MRD Negative

MRD negativity in the marrow (NGF or NGS, or both) and by imaging as defined below, confirmed minimum of 1 year apart. Subsequent evaluations can be used to further specify the duration of negativity (e.g., MRD-negative at 5 years)

6.2.1.2	Flow MRD Negative Absence of phenotypically aberrant clonal plasma cells by NGF on bone marrow aspirates using the EuroFlow standard operation procedure for MRD detection in multiple myeloma (or validated equivalent method) with a minimum sensitivity of 1 in 10^5 nucleated cells or higher
6.2.1.3	Sequencing MRD Negative Absence of clonal plasma cells by NGS on bone marrow aspirates in which presence of a clone is defined as less than two identical sequencing reads obtained after DNA sequencing of bone marrow aspirates using the ClonoSEQ platform (or validated equivalent method) with a minimum sensitivity of 1 in 10^5 nucleated cells or higher
6.2.1.4	Imaging Plus MRD Negative MRD negativity as defined by NGF or NGS plus disappearance of every area of increased tracer uptake found at baseline or a preceding PET/CT or decrease to less than mediastinal blood pool SUV or decrease to less than that of surrounding normal tissue
6.2.2	Standard IMWG Response Category
6.2.2.1	Stringent Complete Response (sCR) CR as defined below plus all of the following: 
• Normal serum FLC ratio at two consecutive times and• Absence of clonal cells in bone marrow by immunohistochemistry or 2- to 4- color flow cytometry.^a• Presence/absence of clonal cells is based upon the κ/λ ratio. An abnormal κ/λ ratio by immunohistochemistry requires a minimum of 100 plasma cells for analysis. An abnormal ratio reflecting presence of an abnormal clone is κ/λ ratio of 4:1 or 1:2.
6.2.2.2	Complete Response (CR) Patients who have complete disappearance of an M-protein and no evidence of myeloma in the bone marrow are considered to have complete response. To be considered CR, patients must meet all of the following criteria: 
• Negative immunofixation on the serum and urine• Disappearance of any soft tissue plasmacytomas• $\leq 5\%$ plasma cells in bone marrow• If the only measurable disease is FLC, a normal FLC ratio of 0.26-1.65
6.2.2.3	Very Good Partial Response (VGPR) 
• Serum M-protein detectable by immunofixation but not quantifiable on electrophoresis AND

- Urine M-protein < 100 mg/24 hours

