9.2.1.2 Secondary Endpoints

- Progression-free survival defined as the time from randomization until the earlier of progression or death due to any cause, or censored at date of last disease evaluation (Note: Only deaths that occur within 3 months of the last disease evaluation are considered events.)
- Best response on treatment for eligible patients based on standard IMWG criteria as described in Section 6; Response rates for eligible patients including very good partial response (VGPR), complete response (CR) and stringent CR (sCR) at 12-, 24-, 36- and 60-cycles post-randomization
- Incidence of adverse events by worst grade and type for treated patients determined using CTCAE; Rates of worst grade 3 or higher non-hematologic toxicity and overall worst grade 3 or higher toxicity on treatment

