9.3.2 Secondary Clinical Analyses

Progression-Free Survival (PFS)

An important secondary aim is to evaluate whether a response-adapted strategy translates into superior progression-free survival for patients switching to more-intensive treatment. PFS will be estimated using the KM method and compared using the stratified log-rank test. Median PFS on the control arm is assumed to be 18 months based on results from recent clinical trials. Assuming exponential distribution of failures, this study is design to detect a 44% increase in median PFS to 26 months on the experimental arm. This corresponds to a treatment HR approximating 0.70 [monthly hazard rate 0.0385 versus 0.0267]. At 1-sided 2.5% type I error, there is approximately 90% power using a log-rank test to detect this HR given 510 patients uniformly accrued over 3.5y with full information of 319 PFS events at 4.5y (accrual end plus one year). The actual timing of this PFS analysis will depend on accrual. The analysis will not be done before one year after the last patient is randomized. No interim analyses for the PFS comparison will be conducted. The study team will also not consider or declare the experimental arm to be a success based on the PFS endpoint alone.

Response

Response will be tabulated by category. Response rates (sCR, CR, VGPR) will be compared using the chi-squared test for proportions. It is hypothesized that the ixazomib-lenalidomide arm will have higher response rates. Ineligible patients are excluded from the analysis and unevaluable patients are counted in the denominator. Sensitivity analyses will exclude unevaluable patients from the rate calculations. Given 255 patients per arm, there is over 90% to detect a difference of 15% in VGPR rates at 1-sided 2.5% significance assuming a 52.5% overall VGPR rate.

Toxicity

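### Response is compared without regard to response at entry: patients already in VGPR or better count as responders in either arm, so precision is given up, and the plan does not say whether its power figure includes them

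*Combined protocol and SAP*

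**What the plan says.** Section 9.2.1.2 defines the endpoint as "Best response on treatment for eligible patients based on standard IMWG criteria as described in Section 6", and adds VGPR, CR and sCR rates at 12, 24, 36 and 60 cycles. Section 6.1 explains that baseline disease values may be unknown, so "we will limit the assessments to categories that are independent of baseline values". VGPR in Section 6.2.2.3 is such a state. Its serum part is "Serum M-protein detectable by immunofixation but not quantifiable on electrophoresis AND"; the second condition is a limit of 100 mg per 24 hours on the M-protein in urine.

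Section 3.2.3 admits a patient with residual disease by central MRD testing or with a monoclonal protein in serum or urine. Nothing excludes a patient in VGPR, CR or sCR. Entry response is not a stratification factor (Sections 4.2.5 and 9.6).

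For the analysis, Section 9.3.2 says "Response rates (sCR, CR, VGPR) will be compared using the chi-squared test for proportions", and "Ineligible patients are excluded from the analysis and unevaluable patients are counted in the denominator". The power statement reads "Given 255 patients per arm, there is over 90% to detect a difference of 15% in VGPR rates at 1-sided 2.5% significance". The rate behind it is named at the end of the same sentence: "assuming a 52.5% overall VGPR rate".

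**The concern.** Patients arrive after induction, transplant and 6 to 18 months of lenalidomide. Some will already be in VGPR or better. For best response of VGPR or better, such a patient is a responder whichever arm is assigned, once the state is confirmed on study. No rule separates these patients, and the test does not use their entry status.

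Two things are at stake. First, precision: patients whose result on this category is settled at entry add variation to both arms and no contrast. Second, meaning: the raw rate mixes response held at entry with response gained on study, and a reader cannot tell whether the 52.5% and the 15 points describe all patients or only those who can still change.

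**Working it through.** **Inputs from the plan (Section 9.3.2).** n = 255 per arm; one-sided 2.5%, so z = 1.96; difference 15 points; overall rate 52.5%. With 1:1 allocation the rates are 52.5 ± 7.5, that is 45% and 60%.

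**Input the plan does not give.** The share b already in VGPR or better at randomization. I use 25%, 30% and 42% as assumptions. The 42% comes from the phase II trial of this combination cited in Section 1.3. There, best responses were sCR 7.8%, CR 26.5% and VGPR 53%, together 87.3% of 64, or about 56 patients. Also, "29 patients had an improvement in their best overall response from their baseline response". So at least 56 − 29 = 27 of 64 (42%) had entered at VGPR or better. That bound belongs to that cohort. It is not described as selected for residual disease, and its VGPR definition is not given.

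**Formula.** Power = Φ{[Δ − z√(2p̄(1−p̄)/n)] / √(p₁(1−p₁)/n + p₂(1−p₂)/n)}.

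**The plan's figure.** (0.15 − 1.96 × 0.0442)/0.0437 = 1.45, so power is 92.6%. The statement of over 90% reproduces.

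**Stratified test.** Patients in VGPR or better at entry are responders in both arms, so their stratum contributes nothing to a Mantel-Haenszel test. Its power is close to that of a comparison of the remaining 255(1−b) per arm.

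**Three readings of the 15 points.**

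1. 45% versus 60% are rates in all patients. Conversion among the rest is then (0.45−b)/(1−b) versus (0.60−b)/(1−b).
2. 45% versus 60% hold only among patients below VGPR at entry. Overall rates are b + 0.45(1−b) and b + 0.60(1−b).
3. The overall rate stays at 52.5%, and the 15 points hold only among patients below VGPR. The overall difference is 0.15(1−b).

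Power, unadjusted / stratified:

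| Entry share b | Reading 1 | Reading 2 | Reading 3 |
|---|---|---|---|
| 25% | 93% / 98% | 76% / 84% | 72% / 86% |
| 30% | 93% / 99% | 71% / 81% | 66% / 86% |
| 42% | 93% / >99% | 59% / 74% | 50% / 92% |

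Worked case, reading 2 at 42%. Overall rates are 0.42 + 0.58 × 0.45 = 68.1% and 0.42 + 0.58 × 0.60 = 76.8%, a difference of 8.7 points. Unadjusted: (0.087 − 1.96 × 0.0396)/0.0394 = 0.24, power 59%. Stratified, with 255 × 0.58 = 148 per arm: (0.15 − 1.96 × 0.0581)/0.0574 = 0.63, power 74%.

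Simulation (40,000 runs) at shares from 30% to 60% agreed with these approximations to within about 1 point for the stratified test and 1.5 points for the unadjusted test.

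**What reading 1 requires.** Conversion of 27% versus 47% at b = 25%, 21% versus 43% at 30%, and 5% versus 31% at 42%. It becomes impossible above 45%, because the control rate would then be lower than the entry share.

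**The case against.** The strongest case for the plan is that Section 9.3.2, read literally, gives rates in all patients. Power is then 92.6% whatever the entry share, and the plan loses nothing against its own claim. That stands: on this reading the unadjusted test only forgoes a gain.

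Three stronger readings are tempting and are not supported.

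- A reader might infer that the endpoint has half its stated power. That needs the 15 points to be confined to patients below VGPR at entry, and an entry share of about 45% (reading 3) to 55% (reading 2). The documents state neither. The 42% is borrowed from a different population: requiring residual disease could lower the share here, and prior maintenance could raise it.
- A reader might infer bias. Randomization balances entry response on average, and the chi-squared test remains valid.
- A reader might infer that the analysis misses its objective because it does not measure deepening. Section 1.2 does speak of depth of response, but Objective 2.2.2 is to evaluate best response on treatment and compare response rates between arms. The planned comparison answers that.

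It is also fair to say that entry responders are uninformative only for best response of VGPR or better. A patient in VGPR at entry can still reach CR. If the rates at 12 to 60 cycles mean status at that time, such a patient can also lose response.

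**Conclusion.** The structural point holds. Patients already in VGPR or better can be randomized, count as best-response responders in either arm, and are compared by a test that ignores entry status. This follows from the definitions taken together; no single sentence says it.

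The size is conditional. On the literal reading, power is as stated, and stratification would raise it from 93% to 98% at a 25% entry share. If the effect is confined to patients below VGPR, unadjusted power is about 71–76% (reading 2) or 66–72% (reading 3) at shares of 25–30%, and about 50–60% at 42%. Stratification improved power in every case in the table but does not always restore 90%: it gives about 74% in reading 2 at 42%. All of this rests on assumed entry shares.

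This is a nearly free improvement and a clarification for a secondary endpoint. It does not touch the overall survival analysis.

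**What to change.** In Section 9.3.2:

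- Compare VGPR-or-better and CR-or-better rates with a Mantel-Haenszel test, or logistic regression, stratified by response status at randomization (below VGPR, VGPR, CR or better).
- Derive that status from the SPEP, UPEP, FLC and immunofixation already required before randomization. CR under Section 6.2.2.2 also needs marrow plasma cells of at most 5% and no soft tissue plasmacytomas, so use the baseline marrow and imaging as well, or define the top stratum as immunofixation-negative. Say whether one baseline set of tests suffices, since Section 6.1.1.4 asks for two consecutive determinations to confirm response.
- Report conversion to VGPR or better among patients below VGPR at entry, and to CR or better among those below CR.
- State the expected share in VGPR or better at entry, and whether the 52.5% rate and the 15-point difference include those patients. State that the VGPR rate means VGPR or better, if so. Restate the power for the chosen contrast.

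The cost is SAP wording and one derived baseline variable, with no new visits, tests or patients. The restated power may be less favourable than the present figure.

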9.2.1.3 Exploratory Endpoints

- Time to progression (TTP) defined as the time from randomization to progression, or censored at date of last disease evaluation
- Duration of response (DOR) defined as the time of observed response (VGPR or better) to the time of progression in the respective group of responders
- Treatment duration calculated as the time from randomization to date off treatment, or censored at the date of last treatment
- Cumulative dose calculated as the sum of all doses taken across all cycles

- Dose intensity calculated as cumulative dose received divided by treatment duration
- Relative dose intensity calculated as the dose intensity divided by planned dose intensity

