Each site must complete a protocol-specific Delegation of Tasks Log (DTL) using the DTL application in the Delegation Log section on the CTSU members' website. The Clinical Investigator (CI) is required to review and electronically sign the DTL prior to the site receiving an Approved site registration status and enrolling patients to the study. To maintain an approved site registration status the CI must re-sign the DTL at least annually and when a new version of the DTL is released; and activate new task assignments requiring CI sign-off. Any individual at the enrolling site on a participating roster may initiate the site DTL. Once the DTL is submitted for CI approval, only the designated DTL Administrators or the CI may update the DTL. Instructions on completing the DTL are available in the Help Topics button in the DTL application and include a Master Task List, which describes DTL task assignments, CI signature, and CTEP registration requirements.

Checking Your Site's Registration Status:

Site's registration status may be verified on the CTSU members' website.

- Click on *Regulatory* at the top of the screen;
- Click on *Site Registration*; and
- Enter the site's 5-character CTEP Institution Code and click on Go

- Additional filters are available to sort by Protocol, Registration Status, Protocol Status, and/or IRB Type.

NOTE: The status given only reflects institutional compliance with site registration requirements as outlined within the protocol. It does not reflect compliance with protocol requirements for individuals participating on the protocol or the enrolling investigator's status with the NCI or their affiliated networks.

Rev. Add3

Patient Enrollment

Patients must not start protocol treatment prior to Step 1 randomization.

Treatment should start within fourteen (14) days after Step 1 randomization.

The Oncology Patient Enrollment Network (OPEN) is a web-based registration system available on a 24/7 basis. OPEN is integrated with CTSU regulatory and roster data and with the LPOs registration/randomization systems or the Theradex Interactive Web Response System (IWRS) for retrieval of patient registration/randomization assignment. OPEN will populate the patient enrollment data in NCI's clinical data management system, Medidata Rave.

Requirements for OPEN access:

- A valid CTEP-IAM account;

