Patients will be registered and randomized through OPEN and assigned patient ID number. This number must be recorded by the registering institution at the time of registration for proper clinical supply dispersion. Once a patient has been registered, ECOG-ACRIN will electronically transmit a clinical drug request for that patient to the PMB. This request will be entered and transmitted by ECOG-ACRIN the day the patient is registered and will be processed by PMB the next business day and shipped the following business day. If a patient is registered on Monday, ECOG-ACRIN would enter a clinical drug request for that patient on Monday and PMB would process that request on Tuesday and ship the drug on Wednesday. Sites could expect to receive their order approximately Thursday or Friday. Shipments to United States sites can be expedited (i.e., receipt on Thursday in example above) by the provision of an express courier account name and number to ECOG-ACRIN at the time the patient is registered/randomized.

The initial patient-specific supply will be enough to complete 8 weeks of treatment (2 x 3-capsule blister cards). The supplies will be sent to the registering investigator / drug shipment investigator at the time of registration and should arrive within 5 to 7 business days. Subsequent orders for blinded, patient-specific supplies must be requested by the Principal Investigator (or his/her authorized designee[s]) for EAA171 at each participating institution using the PMB On-line Agent Order Processing (OAOP) program. The assigned patient ID number (e.g., 999999) and the patient initials (e.g., "FML") should be entered in the "Patient or Special Code" field. A separate order is required for each patient ID number (e.g., 999999) being ordered. All drug orders should

be shipped directly to the physician responsible for treating the patient. Requests can be placed **6 weeks after the last shipment is received**.

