Treatment exposure to the oral medications lenalidomide and ixazomib will be quantified using patient medication calendars. Cumulative dose, dose intensity, and relative dose intensity will be calculated overall and by cycle. Data will be summarized by treatment arm with descriptive statistics and graphically over time. Treatment duration in each arm will be estimated using the Kaplan-Meier method. Patients will be classified into dichotomous groups based on a 75% relative dose intensity cutoff (< 75% vs \geq 75% represents poor vs good treatment adherence). The proportion of patients with poor lenalidomide treatment adherence will be compared between arms using the chi-squared test for proportions. In addition, multivariable logistic regression analysis will be conducted to identify the baseline factors associated with calculated good treatment adherence. We will conduct one interim analysis to monitor treatment adherence to ixazomib. Specifically, the treatment adherence rate at 18 months will be measured by ixazomib relative dose intensity at or exceeding 75% ("good" treatment adherence). This analysis is expected to occur at 2.5 years from randomization when 72 patients (29% of target accrual) have reached potentially 18 months of assigned ixazomib therapy. If the treatment adherence rate is at least 80% we would consider this acceptable while a treatment adherence rate of 65% is considered evidence that adherence to ixazomib is unacceptable. If

54 or more patients achieve target treatment adherence exceeding 75% over 18 months, then the study will continue. If the true treatment adherence rate is 65%, the probability of concluding treatment adherence is acceptable is 0.05 (type I error). If the true treatment adherence rate is 80%, the probability of concluding treatment adherence is acceptable is 0.88 (power).

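### Relative dose intensity counts the drug-free days between randomization and first dose, so patients reduced early to 3 mg can fall on the wrong side of the 75% adherence cut

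*Combined protocol and SAP*

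**What the plan says.** Section 9.2.1.3 builds the exposure measure in four steps:

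- duration: "Treatment duration calculated as the time from randomization to date off treatment, or censored at the date of last treatment"
- numerator: "Cumulative dose calculated as the sum of all doses taken across all cycles"
- ratio: "Dose intensity calculated as cumulative dose received divided by treatment duration"
- scaling: "Relative dose intensity calculated as the dose intensity divided by planned dose intensity"

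The time base of the planned dose intensity is not given.

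Section 4 (Patient Enrollment) fixes when dosing can begin: "Patients must not start protocol treatment prior to Step 1 randomization", and "Treatment should start within fourteen (14) days after Step 1 randomization". Section 8.1.9 provides no blinded starter supply and says that the first patient-specific shipment "should arrive within 5 to 7 business days". The same section's worked example has drug reaching the site on about the Thursday or Friday after a Monday registration.

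Section 9.3.3 (Treatment Exposure) splits patients at 75% relative dose intensity into good and poor adherence. For the single adherence interim, "the treatment adherence rate at 18 months will be measured by ixazomib relative dose intensity at or exceeding 75" percent, and the study continues if at least 54 of 72 patients qualify. The stated type I error is 0.05 at a true rate of 65%, and the stated power is 0.88 at 80%. Section 9.3.4 reuses the adherence groups in the quality-of-life regressions. Section 5.5.1 sets ixazomib/placebo at 4 mg on days 1, 8 and 15 of a 28-day cycle, with 3 mg as the first reduced level.

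**The concern.** The numerator starts at first dose and the denominator at randomization. The days in between reflect shipping and scheduling, not adherence, yet they lower the score.

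This would matter little for a descriptive summary. Here the score is cut at 75% and feeds a continuation rule. The first reduced ixazomib level is 3/4 = 75% of the planned dose, so patients reduced early sit at the cut. The same holds for the first lenalidomide reduction in Section 5.5.2, where 21 of 28 days at an unchanged daily dose is 21/28 = 75%. A small bias can therefore change a patient's class where a less critical cut would absorb it.

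**Working it through.** **1. The plan's own figure.** With X binomial on 72 patients, P(X ≥ 54) is 0.046 at 65% and 0.884 at 80%. The stated 0.05 and 0.88 reproduce.

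**2. Inputs.** The lag L from randomization to first dose is 3 days (shipping example, Section 8.1.9), 7 days (5 business days, same section) or 14 days (the limit in Section 4). The window is 18 months = 18 × 365.25/12 = 547.9 days.

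**3. A patient who takes every 4 mg dose.** Over a fixed window from randomization, relative dose intensity is (547.9 − L)/547.9. The cut on treated time that corresponds to a recorded 75% is 0.75 divided by that factor.

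| L (days) | Recorded value | Effective cut |
|---|---|---|
| 3 | 99.5% | 75.4% |
| 7 | 98.7% | 76.0% |
| 14 | 97.4% | 77.0% |

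Lag alone would bring this patient below 75% only beyond 0.25 × 547.9 = 137 days. The patients who can change class are those whose value from first dose lies between 75% and about 77%.

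**4. Patients reduced to 3 mg who take every prescribed capsule.** Over 19 cycles (532 days) the planned total is 57 × 4 = 228 mg. The value from first dose is mg taken/228. The value from randomization multiplies this by 532/(532 + L).

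| 3 mg given | mg taken | From first dose | L = 7 | L = 14 |
|---|---|---|---|---|
| throughout (limiting case) | 171 | 75.0% | 74.0% | 73.1% |
| after the first capsule | 172 | 75.4% | 74.5% | 73.5% |
| after cycle 1 | 174 | 76.3% | 75.3% | 74.4% |
| after cycle 2 | 177 | 77.6% | 76.6% | 75.6% |

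The first row is a limit, because everyone starts at 4 mg. The first two rows change class at both lags, the third only at 14 days, and the fourth at neither.

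**5. The other end of the clock.** If duration ends at the last ixazomib dose, on day 15 of cycle 19, it is 18 × 28 + 14 + L = 518 + L days. A fully dosed patient then scores 532/(518 + L): 102.7% (L = 0), 101.3% (L = 7) or 100.0% (L = 14). With L = 7 the effective cut is 0.75/1.0133 = 74.0%, below the nominal value. The patient reduced after cycle 1 with a 14-day lag scores 74.4% on one end date and 76.3% on the other.

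**6. The 54-of-72 rule.** The documents give no distribution of relative dose intensity, so the number of patients in the 75–77% band is unknown. Purely as an assumption, if 1%, 2% or 3% of adherent patients were misclassified, power at 80% would be 0.847, 0.803 or 0.753, and type I error at 65% would be 0.036, 0.028 or 0.022. With 0.80 × 72 = 57.6 adherent patients expected, those shares are 0.6, 1.2 and 1.7 patients.

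**The case against.** The strongest reply is that the affected group is very narrow. The patient reduced after cycle 1 clears 75% by 174 − 171 = 3 mg, which is one capsule, so with more than one missed capsule that patient is below the cut on either clock. At a 7-day lag the same patient keeps the good-adherence class, and the shipping example suggests that lags of 3 or 4 days are possible. This stands, and it is why the point is minor. It does not make the formula right: anyone whose value from first dose falls in the band is exposed, whether through dose reduction, missed capsules or both.

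Second, planned dose intensity has no stated time base, and Section 9.3.3 mentions calculation by cycle as well as overall, so the analysts may intend treated time. That is possible, but the written duration starts at randomization and no passage removes the lag.

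Third, both blinded arms share the same start window and supply process, so no differential bias between arms is shown. That stands. So does the point that randomization is a legitimate origin for the Kaplan-Meier summary of treatment duration, matching OS, PFS and TTP.

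A reader might also infer that every patient is understated, or that fully compliant patients on the planned dose drop below 75%. Neither is supported. A same-day start has no lag, the day-15 end date can reverse the bias, and 4 mg throughout gives 97.4% at worst within the 14-day window. One perfect cycle with a 14-day lag does score 28/42 = 66.7%, but only if the measure runs over the patient's own duration, which the 18-month rule does not specify.

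**Conclusion.** The definition is internally mismatched and should be corrected, but the consequence is small. Within the 14-day start window, and with duration ending at the date off treatment, 18-month relative dose intensity is lowered by about 0.5% to 2.6%. Only patients between 75% and about 77% from first dose can change class, typically those on 3 mg from the start or after about one cycle. The alternative end date can offset or reverse the shift, so the defect is inconsistent scoring rather than a uniform downward bias.

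A reader might infer that the adherence rule is seriously compromised, for example that its chance of continuing falls from 88% to 78% or 64%. Those figures follow from assuming that a true 80% is recorded as 78% or 76%, and nothing in the documents links the lag to shifts of that size. The rule's stated operating characteristics are correct for the rate as measured. The effect on it is probably small and cannot be quantified without the distribution of relative dose intensity. The figures here assume lags of 3 to 14 days, 28-day cycles without delay, and planned intensity based on 4 mg three times per cycle.

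**What to change.** In Section 9.2.1.3, and wherever Section 9.3.3 relies on it, define a separate exposure period for dose intensity, relative dose intensity and the 18-month adherence window only:

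- start it at the date of first dose of each drug;
- end it at one common point on the same cycle basis as the planned dose intensity, for example the end of the last cycle started or the date off treatment, with a single choice applied to all patients;
- state the time base of the planned dose intensity, and whether patients who stop before 18 months are scored over the full window or their own duration;
- count randomized patients who never start separately, and say whether they belong to the 72.

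Leave the Kaplan-Meier treatment-duration summary running from randomization. Because 3 mg is exactly 75% of 4 mg, also settle whether a value of exactly 75% qualifies: Section 9.3.3 includes it in one sentence and requires more than 75% in another.

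The cost is a few lines of text before the adherence interim. The medication calendar in Appendix II already records dates and capsules taken, so no new data are needed.
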